## 13. PHARMACOKINETIC / PHARMACODYNAMIC ANALYSES

The primary goal of this analysis is to characterize the pharmacokinetic / pharmacodynamic relationship of GSK2831781 following repeat intravenous and subcutaneous dosing in participants with active ulcerative colitis. The influence of subject demographics and baseline characteristics, including disease activity in this population will be investigated.

### 13.1. Statistical Analyses / Methods

A summary of the planned population pharmacokinetic / pharmacodynamic analyses is outlined below:

- Drug GSK2831781 concentration (or pharmacokinetic parameter) and pharmacodynamic data will be subjected to nonlinear mixed effects modelling using the program NONMEM to develop a population PK/PD model.
- To support this analysis, a PK/PD dataset will be generated. The details for the dataset specifications are provided in a separate document.
- Detailed PK/PD methodology is presented in [Appendix 10: Pharmacokinetic / Pharmacodynamic Analyses](#).

A PK/PD report will be produced by CPMS and presented separately from the main clinical study report (e.g. as an appendix).

## 15. APPENDICES

### 15.1. **Appendix 1: Protocol Deviation Management and Definitions for Analysis Population Exclusions**

As Per-Protocol populations will not be used, participants will not be excluded from analyses due to protocol deviations.

## 15.2. Appendix 2: Schedule of Activities (SoA):

### Double Blind Treatment

WEEK	Screening		Induction Phase					Extended Treatment Phase					Follow-Up 	Early Withdrawal Visit 		
	Pre-dose	Post-dose	2	4 	6	10	12 	14	18 	22 	26 	30	42 			
DAY	-35 to -7 	-14 to -7 	Day 1		15	29	43	71	85	99	127	155	183	211	295	
Window (days)					±2	±3	±3	±3	±5	±3	±3	±3	±3	±3	±7	
Study Population																
Informed Consent	X															
Inclusion/Exclusion Criteria	X															
Demography	X															
Weight	X							X		X			X	X	X	
History  (Medical/Disease/IBD Therapy)	X															
Extra-Intestinal Manifestations History	X															
Smoking status	X						X						X	X	X	
Efficacy																
Determination of 'Normal' stool count for Mayo Score	X															
Endoscopy with Biopsy 		X						X					X		X 	
Mayo (Complete or Partial)	P	C	P	P	P	P	C		P	P	C	P	C	P	C  /P	
Steroid Taper								X								
Extra-Intestinal Manifestations Activity			X				X					X	X	X	X	
Safety Assessments																
Vital Signs	X		X	X 	X 	X	X	X		X 	X 	X	X	X	X	X
12-lead ECG 	X		X	X 				X			X			X	X	X
Full/Brief Physical	F		B	B	B	B	B		B	B	B	B	B	F	F	
Concomitant Medications	X															
AEs / SAEs 																
Haematology 	X		X		X	X	X	X		X	X	X	X	X	X	X
Clinical chemistry (incl. CRP) 	X		X		X	X	X	X		X	X	X	X	X	X	X
Pregnancy Test (WOCBP) 	X		X		X	X	X	X		X	X	X	X	X	X	X

## CONFIDENTIAL

204869

WEEK	Screening		Induction Phase					Extended Treatment Phase					Follow-Up 	Early Withdrawal Visit 		
	Pre-dose	Post-dose	2	4 	6	10	12 	14	18 	22 	26 	30	42 			
DAY	-35 to -7 	-14 to -7 	Day 1		15	29	43	71	85	99	127	155	183	211	295	
Window (days)					±2	±3	±3	±3	±5	±3	±3	±3	±3	±3	±7	
Urinalysis 	X		X		X	X	X	X	X	X	X	X	X	X	X	X
TB – QuantiFERON ± PPD 	X															
Serology (HIV, HBV, HCV, CMV, EBV and VZV)	X															
Clostridium difficile toxin	X															
FSH & oestradiol (if appropriate) 	X															
Dosing and PK/PD																
Randomization			X 													
IMP administration 			IV		IV		IV	IV	SC	SC	SC	SC				
PK 			X	X 	X		X 	X	X	X	X	X	X	X	X	X
sLAG3 			X	X 	X		X 	X	X	X	X	X	X	X	X	X
Blood proteomic signature 			X		X			X								
Blood transcriptomic signature 			X													
LAG3 Cell Depletion (by Flow Cytometry) 			X		X			X					X	X 	X 	
Immunogenicity			X		X	X		X	X	X		X	X	X	X	X
4β-hydroxycholesterol (4βHC) 			X					X								
Faecal Calprotectin 			X		X		X	X		X		X	X	X	X	X
Serum Trypsase 			X			X	X			X		X	X	X	X	X
Patient Reported Outcomes																
IBDQ, FACIT-Fatigue and SF-36 			X				X	X				X	X	X	X	X
Bowel symptom eDiary			<----->													
PGIC & PGIS 			X 				X					X	X	X	X	X
Exit Interview													X 		X 	
Other																
PGx Sample			X													

**Footnotes:**

- 1 See SRM for requirements for data collection.
- 2 Endoscopy should be flexible sigmoidoscopy. However, colonoscopy can be performed at screening if required for assessment of dysplasia risk (see Protocol Section 5.1), and at any timepoint if clinically indicated.
- 3 ECG in triplicate at screening and single at all other time points. See Protocol Section 8.6.3, Electrocardiograms for further detail.
- 4 Collection of SAEs starts from screening whilst collection of AEs will commence from Day 1.
- 5 Unless specified otherwise, all samples will be taken prior to administration of study treatment.
- 6 Negative test required during screening and immediately prior to the first dose of study treatment. A serum pregnancy test is required at screening, after which a highly sensitive urine pregnancy test is adequate. If a urine test cannot be confirmed as negative, a serum pregnancy test is required.
- 7 A PPD test maybe performed following two indeterminate Quantiferon tests to determine TB status, see Protocol Section 5.2.
- 8 To confirm postmenopausal status, serum FSH and oestradiol testing will be performed for all postmenopausal females at the screening visit.
- 9 See Protocol Section 6.2 for details of dosing duration and monitoring period.
- 10 Unless stated, samples taken on a day of dosing must be pre-dose sample (up to 2 hr before the next dose).
- 11 Additional sampling will be required in a subset of participants to characterise SC pharmacokinetics. See Protocol Section 8.3, for schedule.
- 12 LAG3 depletion will only be undertaken in sites where shipping to central lab can be achieved in the required timeframe, see Protocol Section 8.4, and SRM.
- 13 IBDQ, FACIT-Fatigue, SF-36, PGIC and PGIS are to be performed before any other assessments on visit days.
- 14 A 7-day window enables turnaround of centrally read endoscopy score for inclusion to arrange Day 1 visit; however, endoscopy can be performed up to Day -3 if all other criteria for study eligibility have been met by this time and Robarts have agreed rapid turnaround of central endoscopy read.
- 15 PGIC not to be done on Day 1.
- 16 Vital signs to be taken every 30 minutes ( $\pm 5$  minutes) until completion of post dose monitoring period. A single ECG be taken within 4 hours of completion of dose administration. For participants who have discontinued treatment but remain on study, post-dose monitoring does not apply.
- 17 Samples to be taken immediately after end of IV infusion (preferably within 15 minutes).
- 18 Samples to be taken up to 2 hr before the next dose, and one sample immediately after end of IV infusion (within 15 minutes).
- 19 Week 12 visit scheduled to enable recall of Non-Responders to move to Open Label dosing at Week 12, see Open Label Treatment SoA below. Telephone call can be used to ensure Responders initiate steroid taper and cancel scheduled visit for Responders next due to undertake dosing at Week 14.
- 20 In case of Early treatment discontinuation, or study withdrawal, the investigator should undertake a Follow-Up visit approximately 16 weeks after the last dose event to allow safety monitoring following drug washout.
- 21 Participants who discontinue study treatment are encouraged to complete remaining scheduled visits for the treatment phase they are in. However, an Early withdrawal visit is only required for participants who prematurely discontinue study treatment and do not agree to complete the remaining scheduled visits for that phase.
- 22 Complete 4-domain Mayo Score (including Endoscopy) to be performed if withdrawal from study treatment occurs after Week 4 but prior to Week 10 (all participants) or between Week 18 and Week 30 for Responders. The endoscopy is to be performed either at the Early Withdrawal Visit (for participants who do not wish to complete remaining scheduled visits), or at Week 10 or Week 30 (for participants that agree to complete remaining scheduled visits after withdrawing from treatment).
- 23 The window for Screening Visit 1 can be extended to Day -45 where indeterminate test results are returned for assays requiring long central laboratory turnaround times (e.g., QuantiFERON and *C. difficile*). However, if haematology, clinical chemistry and (if applicable) serum pregnancy tests have been

performed outside of the Day -35 window they must be repeated and recorded as an unscheduled visit in the eCRF to confirm eligibility, even if performed at Screening Visit 2.

- 24 Faecal Calprotectin sample may be taken up to 48 hours prior to scheduled visit.
- 25 Exit interview, if applicable, to be undertaken either at Early Withdrawal or Follow-Up.
- 26 Home health care / telemedicine visits may be permitted where applicable country and local regulations and infrastructure allow.
- 27 Randomisation may be performed on Day -1. Randomisation may only proceed when all information pertaining to patient eligibility has been confirmed, including eCRF Mayo score eligibility calculation.
- 28 Samples only to be taken for participants that achieved a responder status at Week 10 and subsequently withdraw from treatment.

## Open Label Treatment

	Open Label Induction Phase				Open Label Extended Treatment Phase						Open Label Follow up 	Open Label Early Withdrawal Visit 	
WEEK	12	14	18	22	24	26	30 	34 	38 	42 	54 		
DAY	85	99	127	155	169	183	211	239	267	295	379		
Window (days)	±5	±3	±3	±3	±3	±3	±3	±3	±3	±3	±7		
Endoscopy with Biopsy				X								X	
Mayo (Complete or Partial)	P	P	P	C			P		P	P	P	C  /P	
Extra-Intestinal Manifestations Activity				X						X	X	X 	
Steroid Taper					X								
Weight				X						X			
Safety Assessments													
Vital Signs	X 	X 	X	X		X 	X 	X	X	X	X	X	
12-lead ECG	X 			X							X	X	
Full/Brief Physical	B	B	B	B		B	B	B	B	B	F	F	
Concomitant Medications	<----->												
AEs / SAEs	<----->												
Haematology 	X	X	X	X		X	X	X	X	X	X	X	
Clinical chemistry (incl. CRP) 	X	X	X	X		X	X	X	X	X		X	
Pregnancy Test (WOCBP) 		X	X	X		X	X	X	X	X		X	
Urinalysis 	X	X	X	X		X	X	X	X	X		X	
Dosing and PK/PD													
IMP administration 	IV	IV	IV	IV		SC	SC	SC	SC				
PK 	X 			X 						X	X	X	
sLAG3 	X 			X 						X	X	X	
Immunogenicity 	X	X		X			X		X	X	X	X	
Faecal Calprotectin 	X		X	X					X	X	X	X	
Patient Reported Outcomes													
IBDQ, FACIT-Fatigue and SF-36 			X	X					X	X	X	X	
Bowel symptom eDiary	<----->												
PGIC & PGIS 				X					X	X	X	X	
Exit Interview										X 	X 		

**Footnotes:**

- 1 Unless specified otherwise, all samples will be taken prior to administration of study treatment.
- 2 A highly sensitive urine pregnancy test is adequate. If a urine test cannot be confirmed as negative, a serum pregnancy test is required.
- 3 See Protocol Section 6.2, for details of dosing durations and monitoring periods.
- 4 IBDQ, FACIT-Fatigue, SF-36, PGIC and PGIS are to be performed before any other assessments on visit days.
- 5 Vital signs to be taken every 30 minutes ( $\pm 5$  minutes) until completion of post dose monitoring period. For participants who have discontinued treatment but remain on study, post-dose monitoring does not apply.
- 6 Additional PK sample immediately after end of IV infusion (preferably within 15 minutes of end of IV infusion).
- 7 In case of Early treatment discontinuation, or study withdrawal, the investigator should undertake a Follow-Up visit approximately 16 weeks after the last dose event to allow safety monitoring following drug washout.
- 8 Participants who discontinue study treatment are encouraged to complete remaining scheduled visits for the treatment phase they are in. However, an Early withdrawal visit is only required for participants who prematurely discontinue study treatment and do not agree to complete the remaining scheduled visits for that phase.
- 9 A single ECG to be taken any time within post-dose monitoring period
- 10 Faecal Calprotectin sample may be taken up to 48 hours prior to scheduled visit.
- 11 Exit interview, if applicable, to be undertaken either at Early Withdrawal or Follow-Up.
- 12 Home health care / telemedicine visits may be permitted where applicable country and local regulations and infrastructure allow.
- 13 Complete 4-domain Mayo Score (including Endoscopy) to be performed if withdrawal from study treatment occurs after Week 16 but prior to Week 22 (all participants). The endoscopy is to be performed either at the Early Withdrawal Visit (for participants who do not wish to complete remaining scheduled visits), or at Week 22 (for participants that agree to complete remaining scheduled visits after withdrawing from treatment).

## 15.3. Appendix 3: Assessment Windows

### 15.3.1. Definitions of Assessment Windows for Analyses

Note that assessment windows will be applied on an endpoint by endpoint basis.

Early Withdrawal and Unscheduled visits will be assigned to assessment windows according to actual dates rather than the nominal visit labels recorded against the observation.

A window around a target Study Day will typically include all days from the midpoints between it and the target Study Days of the previous and the proceeding visits. In general, the nominal target Study Day for week w is  $(7 * w) + 1$ . The window around the last visit prior to follow up will be symmetrical so that it will be determined by the midpoint between it and the previous visit.

If using assessment windows leads to more than one observation being allocated to a visit then the closest observation to the target date will be taken. If the difference between the two observations is the same, the latest will be used.

If an Early Withdrawal or Unscheduled assessment for any given parameter is allocated to a visit that contains multiple planned time assessments for said parameter, then it will be labelled as “Unscheduled/EW” in summary tables.

Note that all observations will be listed and used for calculation of ‘worst case’ outputs for safety (for example “Summary of Worst-Case Chemistry Results by PCI Criteria Post Baseline Relative to Baseline”).

#### **Assessment windows do not cross study phases**

An exception to the general rule of allocating observations to the nearest visit concerns the transition between study phases. Assessment windows should not allocate a visit to a study phase until the study phase begins for that participant (i.e. the Study Day that they receive their first dose for that study phase).

For example, even if an Unscheduled visit on Week 13 for a responding participant is closest to the first visit for the Extended Treatment Phase, the observations from the Unscheduled visit would be allocated to the Induction Phase because the Extended Treatment Phase has not started.

#### **Screening and Post dose records:**

The post-dose records will be summarized under the last study phase in which participants received a dose. The visit windowing algorithm will be based on the following:

1. CRF assessments/events collected after ‘Last Dose Date + 16 Weeks (+ 7 days)’ (i.e. post-treatment study phase) will not be analysed/summarised. These records will only be listed.

2. For CRF assessments/events collected after Last Dose Date but before ‘Last Dose Date + 16 Weeks (+ 7 days)’:
  - a) All records collected in event datasets will be summarized as well as listed (e.g. AE, CM).
  - b) All records collected for any other assessments will be included for ‘Worst-Case’ summaries (e.g. LABs, Mayo score/endpoints etc).
  - c) Unless stated otherwise, all records for any other assessments will be included in visit-based summaries as described in two scenarios below –
    - i. The visits collected in the same study phase will be summarized against the visit in CRF or using windowing RAP algorithm for ‘Unscheduled’.
    - ii. The visits collected in subsequent study phases will be windowed as ‘Follow-up IND/ETP’ visit (even CRF collected scheduled visits will be mapped). For summaries, the latest assessment among ‘Follow-up IND/ETP’ will be used.

Note that after the final visit (Week 30 / OL Week 42) the next visit would be the Follow-Up and it is not expected that a participant would have an Early Withdrawal visit after these visits.

Target Day	Analysis Window (Days)		Analysis Timepoint
	Beginning Timepoint	Ending Timepoint	
Note: Windowing applies to all domains except Extra Intestinal Manifestations of UC.			
1	1	2	DAY 1
15	3	22	WEEK 2
29	23	36	WEEK 4
43	37	57	WEEK 6
71	58	A day prior to participant's first dose of next phase. For participants who do not take a subsequent dose, maximum of 'Week 10 dosing date +3' and day 85	WEEK 10
99* (First Dose of Period + 1)	Participant's first dose of ETP	102* (First dose of Period + 4)	WEEK 14
127* (First dose of Period + 29)	103* (First dose of Period + 5)	141* (First dose of Period + 43)	WEEK 18
155* (First dose of Period + 57)	142* (First dose of Period + 44)	169* (First dose of Period + 71)	WEEK 22

Target Day	Analysis Window (Days)		Analysis Timepoint
	Beginning Timepoint	Ending Timepoint	
183* (First dose of Period + 85)	170* (First dose of Period + 72)	197* (First dose of Period + 99)	WEEK 26
211* (First dose of Period + 113)	198* (First dose of Period + 100)	225* (First dose of Period + 127)	WEEK 30
85* (First Dose of Period + 1)	Participant's first dose of OL	92* (First dose of Period + 8)	OL WEEK 12
99* (First dose of Period + 15)	93* (First dose of Period + 9)	113* (First dose of Period + 29)	OL WEEK 14
127* (First dose of Period + 43)	114* (First dose of Period + 30)	141* (First dose of Period + 57)	OL WEEK 18
155* (First dose of Period + 71)	142* (First dose of Period + 58)	A day prior to participant's first dose of OL ETP. For participants who do not take a subsequent dose, maximum of 'OL Week 22 dosing date +3' and day 197	OL WEEK 22
183* (First Dose of Period + 1)	Participant's first dose of OL ETP	186* (First dose of Period + 4)	OL WEEK 26
211* (First dose of Period + 29)	187* (First dose of Period + 5)	225* (First dose of Period + 43)	OL WEEK 30
239* (First dose of Period + 57)	226* (First dose of Period + 44)	253* (First dose of Period + 71)	OL WEEK 34
267* (First dose of Period + 85)	254* (First dose of Period + 72)	281* (First dose of Period + 99)	OL WEEK 38
295* (First dose of Period + 113)	282* (First dose of Period + 100)	309* (First dose of Period + 127)	OL WEEK 42
* For delayed first dose in the study phase : - If the first dose of a study phase is within the first visit window of that study phase, then use the number outside brackets in each subsequent window. - If the first dose of a study phase is post-ending timepoint of the first visit window of that study phase, then use the bracketed derivation in each subsequent window.			

## 15.4. Appendix 4: Treatment Phases and Study Phases

### 15.4.1. Treatment Phases

The table below defines treatment phases. Note that if a participant receives study drug at all visits and completes the study, all visits will be categorised as 'on-treatment' including the follow-up visit. Note: follow-up visits for participants who early withdraw in Double Blind Induction and for participants who early withdraw in other study phases without completing all protocol-defined visits in that phase will not be summarised (they will be listed).

Where treatment is discontinued during the study (i.e. the 'study treatment discontinuation' form has been completed in the eCRF), the Study Treatment Stop Date will be defined as the date that the last treatment was given.

Treatment Phase	Definition
Pre-Treatment	Date < Study Treatment Start Date
On-Treatment	Study Treatment Start Date ≤ Date ≤ Study Treatment Stop Date + 16 weeks (+ 7 days, the visit window)
Post-Treatment	Date > Study Treatment Stop Date + 16 weeks

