#### 15.4.2.1. Study Phases for Adverse Events

If a participant discontinues treatment (i.e. the 'study treatment discontinuation' form has been completed) but continues to attend visits AEs will be associated with the study phase until 16 weeks (+7 days) after the last dose. If an AE onset date is during the post-treatment period the AE will not be summarised against a study phase.

If an AE onset date is in one phase and resolution date is in a subsequent phase, the AE will be associated with the phase in which the AE starts. AEs that cross phases where the maximum severity is greater than the severity at onset will be listed separately.

Following the standard rules for summarising AEs, if an AE of a category repeats in the same study phase this will be counted once in that phase, however if the same AE repeats in a subsequent phase, it will be counted in both the first phase and the subsequent phase because AEs in each study phase are summarised in separate tables.

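### SAP 15.4.1 starts Post-Treatment seven days before On-Treatment ends, so AEs with onset on days 113–119 fall under conflicting rules; its day-119 limit also leaves some protocol-compliant Follow-Up visits out of the summaries

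*SAP*

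**What the plan says.** The treatment-phase table in SAP 15.4.1 closes On-Treatment at "Study Treatment Stop Date + 16 weeks (+ 7 days, the visit window" and, in the next row, opens Post-Treatment at "Date > Study Treatment Stop Date + 16 weeks". For participants who discontinue, "the Study Treatment Stop Date will be defined as the date that the last treatment was given". For participants dosed at every visit who complete the study, the same section states that "all visits will be categorised as 'on-treatment' including the follow-up visit".

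SAP 15.4.2.1 covers participants who stop treatment but keep attending visits: "AEs will be associated with the study phase until 16 weeks (+7 days) after the last dose". The following sentence is general: "If an AE onset date is during the post-treatment period the AE will not be summarised against a study phase".

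SAP 15.3.1 (post-dose records) has two date rules. Under rule 1, records collected after the last dose date plus 16 weeks plus 7 days "will not be analysed/summarised. These records will only be listed", and that period is labelled the post-treatment study phase. Under rule 2, records before the same date go into the summaries: event data under 2a, worst-case and visit-based summaries under 2b and 2c.

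The protocol schedule (Section 1.3) sets the last subcutaneous dose at Day 183 ±3 and Follow-Up at Day 295 ±7 in the double-blind part. The open-label days are 267 ±3 and 379 ±7.

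**The concern.** Adjacent phases should share one boundary. Here the two rows differ by the 7-day allowance, no precedence rule is given, and 15.4.2.1 attaches opposite consequences to the two phases. Two programmers who both follow the text could therefore produce different AE tables for late onsets. Those events are collected, because Protocol 8.7.1 runs AE collection to the Follow-Up visit. AE incidence is a primary endpoint for induction and a secondary endpoint for the double-blind extended phase.

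The second issue is the length of the allowance. Seven days matches the window around the Follow-Up visit, but the clock starts at the actual last dose, which has its own ±3-day window. A visit that complies with the protocol can then fall beyond the SAP limit, and its laboratory, ECG and vital-sign results would be listed but left out of the summaries.

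**Working it through.** Inputs: the two phase limits (SAP 15.4.1); the AE rules (15.4.2.1 and 15.4.3); the record rules (15.3.1); visit days and windows (Protocol 1.3). The stop date is taken as the date of the last dose, as 15.4.1 states for discontinuers and 15.3.1 uses throughout.

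1. **The plan's own interval.** 295 − 183 = 112 days and 379 − 267 = 112 days; 112 / 7 = 16 weeks. This reproduces the protocol's 16-week Follow-Up.

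2. **Overlap.** On-Treatment ends at 16 × 7 + 7 = day 119. Post-Treatment is any day after 16 × 7 = 112, so it starts on day 113. Days 113–119 satisfy both rows: 119 − 113 + 1 = 7 days.

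3. **An AE with onset on day 115, followed through the rules.**
   - 15.4.1: 115 ≤ 119, so On-Treatment; 115 > 112, so also Post-Treatment.
   - 15.4.3: onset in the On-Treatment period, so treatment-emergent.
   - 15.4.2.1, first sentence: within 16 weeks + 7 days, so it belongs to the study phase.
   - 15.4.2.1, second sentence: onset in the post-treatment period as 15.4.1 defines it, so not summarised against a phase.
   - 15.3.1, rule 2a: before the + 7-day limit, so summarised.

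4. **Permitted gap from last dose to Follow-Up.** Shortest: 288 − 186 = 102 days. Longest: 302 − 180 = 122 days. With dose shift d from −3 to 3 and Follow-Up shift f from −7 to 7, gap = 112 + f − d over 7 × 15 = 105 pairs.

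5. **Compliant visits beyond day 119.** These need f − d ≥ 8:
   - d = −3: f = 5, 6, 7 (3 pairs)
   - d = −2: f = 6, 7 (2 pairs)
   - d = −1: f = 7 (1 pair)

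   The total is 6 of 105 pairs, with gaps of 120–122 days. Example: a dose on Day 180 ends On-Treatment at 180 + 119 = Day 299, so compliant visits on Days 300–302 are listed only. With the dose on schedule, 183 + 119 = Day 302, the last permitted Follow-Up day, and no visit is lost. The open-label counts are identical (267 + 119 = Day 386).

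6. **Correcting the Post-Treatment row alone.** With Post-Treatment starting after day 119, the overlap falls from 7 days to 0. The 6 of 105 pairs remain outside; a limit of 122 days brings that to 0.

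7. **Day 119 itself.** Rule 1 of 15.3.1 applies after the limit and rule 2 before it, so day 119 is in neither.

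**The case against.** The best reply is that this is a drafting slip with a recoverable intention. The On-Treatment row, the first sentence of 15.4.2.1 and both date rules in 15.3.1 carry the 7 days; one row omits them. That is the likely cause. It does not make the text consistent, and correcting that row does not deal with days 120–122.

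On those days, it can be said that a miss needs an early last dose and a late Follow-Up together, and that the completer statement in 15.4.1 is the specific rule for these participants. The first part stands: it is an edge case. The second is a fair reading, but 15.3.1 gives a date rule with no exception for completers. The general remark in 15.3.1 that all observations feed the worst-case outputs does not settle it either, because rule 1 of the same section says otherwise for records after the limit.

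Four stronger readings are tempting, and the documents do not support them:

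- **Concomitant medication is doubly classified.** It is not. 15.4.2.2 ties both the concomitant and the post-treatment categories to the end of On-Treatment, so a start on day 115 is concomitant only.
- **Treatment emergence is ambiguous.** It is not. 15.4.3 tests only whether onset falls in the On-Treatment period.
- **A Follow-Up visit on days 113–119 is both summarised and excluded.** By symmetry 49 of the 105 pairs have f − d ≥ 1, so 49 − 6 = 43 (41%) fall on days 113–119. That counts a double phase label. 15.3.1 does not exclude those records, and rule 2 summarises them up to day 118.
- **Findings are lost.** Records beyond the limit are still listed.

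The visit issue concerns only participants who completed their scheduled visits. 15.4.1 separately says that Follow-Up visits of early withdrawals are listed only (in other phases, where the phase's visits were not all completed).

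**Conclusion.** The plan contradicts itself in two places. First, AEs with onset on days 113–119 after the last dose are assigned to a study phase and barred from its summary by consecutive sentences, and 15.3.1 places the post-treatment cut elsewhere than 15.4.1. Second, a completer whose last dose was 1–3 days early can have a compliant Follow-Up on days 120–122 that 15.3.1 only lists, against the completer statement in 15.4.1.

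The overlap is exactly 7 days. The visit problem covers 6 of 105 permitted day-pairs. The documents give no distribution of actual dosing and visit days, so this cannot be read as a share of patients, and they do not show how many AEs start in the overlap. The effect is small and limited to late safety summaries.

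**What to change.** 1. In SAP 15.4.1, add the 7 days to the Post-Treatment row, so that it starts on the day after On-Treatment ends (any date later than stop date + 16 weeks + 7 days). This removes the AE conflict in 15.4.2.1 and aligns the row with 15.3.1.
2. In 15.4.1 and 15.3.1, state that a completer's Follow-Up visit within its protocol window (at most 122 days after the last dose) is on-treatment and summarised. Tying this to the protocol window matters: a nominal Follow-Up day would not bring these visits in, and the actual visit date without a cap would let a very late visit extend On-Treatment indefinitely.
3. In rule 2 of 15.3.1, replace before with on or before, so that day 119 is covered.

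No change to 15.4.2.2 is needed. The cost is one table row and a few words in two sections, with no new data or analysis. The downside is that a few records up to 122 days after the last dose count as on-treatment.
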